### 7.8.2. Urine Sample Collection

Urine will be collected from each subject at Cycle 1 Day 15 predose and then after administration of INCB059872. The predose sample should be kept separate from the rest of the samples collected. Total urine will be collected over a 6-hour interval after study drug administration. Urine containers should be kept at reduced temperature (refrigerated or ice bath) during collection. After the interval, urine should be mixed thoroughly. The total urine volume and the pH should be measured and recorded in the individual eCRF. Shipping and handling instructions will be provided in the Laboratory Manual; samples will be analyzed by the sponsor or its designee for parameters described in [Appendix C](#).

### 7.8.3. Bioanalytical Methodology and Analysis

The plasma samples will be analyzed for INCB059872 by a validated liquid chromatography–tandem mass spectrometry assay. If there is sufficient urinary excretion of unchanged INCB059872 for assay, the urine samples will be assayed for INCB059872 by a validated assay.

Pharmacokinetic parameters that will be analyzed are shown in [Appendix C](#), and the analysis methodology is described in Section [9.4.2](#).

### 7.8.4. Food-Effect Pharmacokinetic Testing

Pharmacokinetic testing for food effect on drug exposure will be performed on approximately 8 subjects enrolled in TG B1, Part 2; this will occur on Cycle 2 Day 1.

Subjects will have been fasted from food (not including water) for at least 4 hours. A standardized high-fat, high-calorie breakfast will be given to these subjects approximately 30 minutes before administration of study drug. Subjects must consume the entire breakfast within 25 minutes, and INCB059872 administration will begin 5 minutes after completing breakfast.

A high-fat, high-calorie meal (approximately 800-1000 calories, approximately 50% calories from fat) ([FDA 2002](#)) may consist of the following:

- 2 eggs fried in butter
- 2 strips of bacon
- 1 English muffin with butter
- 4 oz hash brown potatoes
- 8 oz whole milk

Alternative menus with the same caloric and fat content may be substituted with the prior approval of the study sponsor.

## **7.10. Other Study Procedures**

### **7.10.1. Distribution of Subject Reminder Cards**

Subjects will be provided with a reminder card at each visit. The subject reminder card will indicate the date/time of the next visit, and will also remind the subject that they should not take

their morning dose of study drug on Days 1, 8, 15, or 22 of Cycle 1 and then Days 1 and 15 for all other cycles, as they will take it after blood draws for safety evaluation have been completed. The reminder cards will have an area on which the date and time of the last dose taken (from the previous evening) and the time of their last meal before the visit should be recorded.

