#### **Study Schedule/Procedures:**

Subjects will have regularly scheduled study visits at the clinical site as part of a 28-day cycle. Study visits are as follows:

- Screening: Day -28 through Day -1
- Cycle 1: Day 1, 4, 8, 11, 15, 22
- Subsequent cycles: Day 1 ( $\pm$  2 days; note that Day 1 must be a day with INCB059872 treatment) and Day 15 ( $\pm$  2 days)
- End of treatment: Subjects must be seen and have blood drawn 2 times per week for 2 weeks after last dose.
- Safety follow-up: 30 days (+ 5 days) after the EOT visit or last dose of study drug if EOT visit not performed (or until toxicities resolve, return to baseline, are deemed irreversible, or the subject receives another anticancer therapy, whichever is shorter).

- Follow-up for disease status (only for subjects who discontinue for reasons other than disease progression).

Laboratory tests for safety

Study visits will include sample collection for hematology, chemistry, coagulation, lipid panel, and urinalysis. Additionally, the screening visit will include serology and fertility/pregnancy testing.

Laboratory tests for PK

Pharmacokinetic [REDACTED] samples will be collected at planned visits and shipped to the sponsor or designee for analysis.

Clinical assessments

Adverse event assessments, vital signs, ECG, physical examination, ECOG performance status, and disease response assessments will be performed by the investigative site.

An objective assessment of disease status will be performed as screening, appropriate to the malignancy type (eg, CT or MRI, bone marrow biopsy/aspirate, peripheral blood, as applicable by tumor type).

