## **5. TREATMENT**

INCB059872 will be self-administered orally QOD or QD on a 28-day cycle. In each cycle of the QOD dosing schedule, subjects should receive 14 doses of INCB059872. In each cycle of the QD dosing schedule, subjects should receive 28 doses of INCB059872. Tablets will be available in 1 mg strength. The initial starting dose for Part 1 will be 2 mg QOD. The initial starting dose for other parts of the study will be based on the aggregate data review of Part 1.

For QOD administration, if a dose is missed by more than 24 hours, the subject should skip the dose and take the next scheduled dose at the usual time. For QD administration, if a dose is missed by more than 4 hours, the subject should skip the dose and take the next scheduled dose at the usual time. INCB059872 tablets should be taken on an empty stomach if possible (refrain from food consumption during the period 2 hours before and 1 hour after taking INCB059872). For subjects participating in the food-effect portion of the study in Part 2, TG B1, a high-fat, high-calorie meal will be consumed within 30 minutes before taking INCB059872 on Cycle 2 Day 1.

Alternative dosing regimens (ie, QD) may be explored based on emerging PK/█ and safety data.

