**Table 7: Schedule of Assessments (Continued)**

Procedure	Protocol Section	Screening	Treatment						EOT	Follow-Up		Notes
			Cycle 1			Cycles 2+				Safety	Disease Status	
		Days -28 to -1	Day 1	Day 8 (± 2 Days)	Day 15 (± 2 Days)	Day 22 (± 2 Days)	Day 1 (± 2 Day)	Day 15 (± 2 Days)		30 Days (+5 Days)	Every 8-9 Wks	
Administer INCB059872 at site	N/A		X	X*	X*	X*	X**					* Subjects should not take drug at home but must bring medication; they will take their dose after initial PK blood draw. NOTE: Drug is not given on Day 8, but if on a dosing day, subject should follow rules above. ** TG B1 subjects for food-effect study.
Assess compliance	5.3			X	X	X	X	X	X			
Administer ATRA at site			X*	X*	X*	X*						* 45 mg/m  per day administered as 2 evenly divided doses; AM dose only in the clinic.
Administer azacitidine at site			X*	X*	X*	X*	X*					* 75 mg/m  SC or IV for 7 days during the first 9-day or less period (ie, a 2-day break allowed on weekend, if needed) of each 28-day treatment cycle.
Administer nivolumab at site			X*		X*		X*	X*				* 3 mg/kg Q2W.
Distribute reminders	7.10.1	X	X	X	X	X	X	X				

CT = computed tomography; [REDACTED]; MRI = magnetic resonance imaging; [REDACTED]; [REDACTED]

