**Table 8: Schedule of Laboratory Assessments**

Local Laboratory Tests	Protocol Section	Screening	Treatment						EOT	Safety Follow-Up	Notes			
			Cycle 1			Cycles 2+								
			Day 1	Day 8 (± 2 Days)	Day 15 (± 2 Days)	Day 22 (± 2 Days)	Day 1 (± 2 Day)	Day 15 (± 2 Days)						
Serum chemistries	Table 9	X	X*	X	X	X	X	X	X	X	* May be performed 3 days before the first dose.			
Hematology*	Table 9	X	X**	X	X	X	X	X	X***	X	* Must be drawn twice a week for the first 2 weeks of study treatment. In addition to Cycle 1 Day 1 and Cycle 1 Day 8, hematology samples should be drawn at Cycle 1 Day 4 ± 1 day and Cycle 1 Day 11 ± 1 day. ** May be performed 3 days before the first dose. *** Must be drawn twice a week for 2 weeks after last dose.			
Lipid panel	Table 9	X	X	X	X	X	X	X	X	X				
Coagulation panel	Table 9	X					X*		X		* Cycle 2 Day 1 and then every 3 cycles thereafter.			
Hepatitis screening	Table 9	X												
Urinalysis	Table 9	X					X*				* Cycle 2 Day 1 and then every 3 cycles thereafter			
Pregnancy test	Table 9	X*	X**						X**		All female subjects of childbearing potential. * Serum ** Urine			
PK plasma (predose)	7.8.1		X	X	X	X	X*				Collect before morning dose of study drug. * Cycle 2 Day 1, only for food-effect testing in Part 2.			
PK plasma TIMED (postdose)	7.8.1.1		X*		X*		X**				* Collect at 0.5, 1, 2, 4, and 6 hours after INCB059872 dose. Excess sample will be used for [redacted] analysis. ** Cycle 2 Day 1 only for food-effect study.			

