### **7.5.4. Electrocardiograms**

All 12-lead ECGs will be performed with the subject in a recumbent or semirecumbent position after 5 minutes of rest. A single ECG is performed at the screening, EOT, and safety follow-up visits. Triplicate ECGs are performed on Cycle 1 Day 1 and Cycle 1 Day 15 at predose and 1, 2, and 6 hours postdose. A triplicate ECG is performed on Cycle 1 Day 8 approximately 24 hours after the last dose on Day 7; if a subject is being seen on Day 7 or Day 9 (study drug administration days), triplicate ECG should be performed before study drug administration. Note that triplicate ECGs should be performed with a 2- to 5-minute break between evaluations. Note that the timed schedule may change per emerging PK data.

The 12-lead ECGs will be interpreted by the investigator at the site to be used for immediate subject management; all ECGs will be collected and reviewed by a central ECG vendor. The decision to include or exclude a subject or withdraw a subject from the study based on an ECG flagged as "Abnormal, Clinically Significant" is the responsibility of the investigator, in

consultation with the sponsor's medical monitor, as appropriate. Clinically notable abnormalities that are considered clinically significant in the judgment of the investigator are to be reported as AEs.

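### For every-other-day (QOD) subjects, the reminder card and Table 7 can be read as calling for doses on non-dosing Days 8 and 22, and the Day 15 window lets the timed PK, urine and ECG visit fall on a non-dosing day

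*Protocol*

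**What the plan says.** **Schedule.** Protocol Section 5: "In each cycle of the QOD dosing schedule, subjects should receive 14 doses of INCB059872"; the QD figure is 28. Section 7.5.4 places the Day 8 ECG about 24 hours after the Day 7 dose and adds: "if a subject is being seen on Day 7 or Day 9 (study drug administration days), triplicate ECG should be performed before study drug administration".

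**Reminder card.** Section 7.10.1 says subjects should not take "their morning dose of study drug on Days 1, 8, 15, or 22 of Cycle 1", and gives the reason: "as they will take it after blood draws for safety evaluation have been completed". It does not separate QD from QOD subjects.

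**Table 7, row for on-site INCB059872.** Cycle 1 Days 1, 8, 15 and 22 are all marked. The footnote to Days 8, 15 and 22 has subjects bring their medication and dose after the first PK draw. It then adds, for one day only: "NOTE: Drug is not given on Day 8, but if on a dosing day, subject should follow rules above". Day 22 has no such exception.

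**PK samples.** Table 8 lists predose plasma on Cycle 1 Days 1, 8, 15 and 22, with the note "Collect before morning dose of study drug". Table 10 asks for a predose sample alone on Days 8 and 22, and for a full profile to 6 hours on Day 15.

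**Day 15.** This visit (± 2 days) carries the timed PK profile (Section 7.8.1.1), the 6-hour urine collection (Section 7.8.2) and triplicate ECGs before the dose and at 1, 2 and 6 hours after it (Section 7.5.4). Section 7.8.1.1 puts study drug administration between the trough sample and the timed samples. The only rule tying a visit to a dosing day is in the Synopsis schedule, for Day 1 of cycles after the first: "note that Day 1 must be a day with INCB059872 treatment".

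**The concern.** Under the QOD calendar, Days 8 and 22 are off days. The card nevertheless tells every subject that a dose will be taken at those visits, and Table 7 marks one on Day 22. The Day 8 exception suggests that the conflict was seen for that day and not carried through to Day 22 or to the card.

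QOD applies to TG A2, B1 and B2 (Section 4.1.2), to TG E at its starting regimen (Section 4.1.3), and to the Part 1 QOD cohorts. An off-schedule dose on Day 8 or 22 falls inside the 28-day DLT period of Section 5.4.3. Cycle 1 DLTs drive the 3 + 3 decisions in Parts 1 and 3 and the Part 2 enrollment stop (5 or more of the first 15 subjects). Those counts are meant to describe the assigned regimen.

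The Day 15 visit raises a different problem. If it falls on an off day, either there is no dose to profile and the PK, urine and ECG data are lost, or a dose is given off schedule to rescue the procedures.

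**Working it through.** **Step 1. Reproduce the 14 doses.** Dosing every other day from Day 1 gives Days 1, 3, 5, ..., 27, which is (27 − 1)/2 + 1 = 14 doses, as Section 5 states. Section 7.5.4 confirms the odd-day pattern by naming Days 7 and 9 as administration days. The 75% evaluability threshold also agrees: 0.75 × 14 = 10.5, rounded up to the protocol's 11.

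**Step 2. Check each visit and its ± 2 day window against that calendar.**

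| Nominal visit | Window | Dosing days | Non-dosing days | Nominal day |
|---|---|---|---|---|
| Day 8 | 6–10 | 7, 9 | 6, 8, 10 | off |
| Day 15 | 13–17 | 13, 15, 17 | 14, 16 | dosing |
| Day 22 | 20–24 | 21, 23 | 20, 22, 24 | off |

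Day 1 of Cycle 2 is study day 29, an odd day, so the calendar carries over.

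**Step 3. Compare the passages for QOD subjects.**

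| Day | Section 5 calendar | Section 7.10.1 card | Table 7 |
|---|---|---|---|
| 8 | no dose | dose at visit | no dose, unless the visit falls on a dosing day |
| 22 | no dose | dose at visit | dose at site, no exception |

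**Step 4. Count doses on a literal reading.** This assumes that the odd-day doses continue unchanged.

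- Extra dose on Day 22 only: 14 + 1 = 15; 15/14 = 1.07, or 7% more. Days 21, 22 and 23 are then consecutive dosing days.
- Extra doses on Days 8 and 22: 14 + 2 = 16; 16/14 = 1.14, or 14% more.

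**Step 5. Day 15.** Two of the five permitted days, 14 and 16, have no scheduled dose. The Table 10 footnote on rescheduling PK covers dose interruption, not a visit on an off day.

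**Step 6. Time since last dose for the samples labelled predose.** On an even day, including nominal Days 8 and 22, a QOD sample is drawn about 24 hours after the last dose. On Day 7, 9, 21 or 23 it is drawn at about 48 hours. One label therefore covers two different times.

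**The case against.** The card is mainly an instruction to withhold the home dose. It serves QD subjects, for whom Days 8 and 22 are real dosing days, and *their morning dose* presupposes that one is due. Section 5 fixes 14 doses, so a site would have to override the assigned schedule to give a fifteenth. This stands as a reason to call the extra doses possible rather than certain. It does not remove the conflict, because the card gives as its reason that the dose will be taken at the visit and has no condition for QOD subjects.

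Table 7 already deals with Day 8, and Section 7.5.4 agrees with it. That stands: Table 7's own defect is Day 22, and Day 8 is at issue only because the card contradicts the Table 7 note.

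Nominal Day 15 is a dosing day, and Section 7.8.1.1 cannot be followed without a dose, so a careful site would avoid Days 14 and 16. This also stands in part. The number of eligible days says nothing about how often visits would fall on them. The window still permits those days, and the condition written for Day 1 of later cycles is absent here.

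A reader might infer that the Cmin endpoint is corrupted. The documents do not support that. No section says that Day 8 or 22 samples feed Cmin. Appendix C defines it as the minimum within the dosing interval, the nominal Day 15 predose sample is already a 48-hour QOD trough, and Section 7.8.1 records sample and last-dose times. The levels would also be close to zero. With the projected Cmax of 0.05 µM at 2 mg and half-life of about 3 hours (Section 1.2.2), and assuming single-exponential decay, 50 nM × 2^(−24/3) ≈ 0.2 nM at 24 hours and 50 nM × 2^(−48/3) < 0.001 nM at 48 hours. A large ratio between two such values carries little weight.

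Finally, Part 1 QOD escalation had stopped by the July 2017 data cutoff (Section 1.6.2). New wording mainly helps the expansion and nivolumab groups.

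**Conclusion.** The inconsistency is real and limited to QOD subjects. The card conflicts with Section 5 on Days 8 and 22 and with Table 7's note on Day 8. Table 7 conflicts with Section 5 on Day 22. The literal consequence is 15 or 16 doses instead of 14 within the DLT window, provided the odd-day doses continue and the site does not read the text as applying only when a dose is due. The Day 15 window separately allows two days on which the timed PK, urine and ECG procedures have no scheduled dose.

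A reader might go further and infer that the extra doses will occur, or that they would produce DLTs because QD escalation in TG B was halted for DLTs (Section 1.6.2). The documents support neither. The wording permits extra doses without compelling them, and one or two added doses are not a QD regimen. The reason to act is that unplanned consecutive-day dosing, or a lost Day 15 profile, should not arise from a drafting conflict that a few words can remove.

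**What to change.** 1. Reconcile Table 7, Section 7.10.1 and Section 5 by schedule, QD and QOD separately, so that they say the same about Days 8 and 22. Which dosing rule applies is for the sponsor to settle; none is proposed here.
2. Extend the visit-scheduling condition that the Synopsis sets for Day 1 of later cycles to the Cycle 1 Day 15 timed PK, urine and ECG visit, so that it falls on a day when a dose is already scheduled.
3. In the PK analysis (Protocol Section 9.4.4 and SAP Section 8), classify Day 8 and Day 22 samples by actual time since last dose, which Section 7.8.1 already collects, and not by the nominal predose label. A single fixed time label would not do, because visits on Days 7, 9, 21 or 23 give 48-hour samples and visits on even days give 24-hour samples.

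The cost is wording in these sections and tables and on the card. No visits or samples are added. The one downside is slightly less flexibility in scheduling Day 15 for QOD subjects.

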## **8. SAFETY MONITORING AND REPORTING**

### **8.1. Adverse Events**

#### **8.1.1. Definitions**

For the purposes of this Protocol, an AE is defined as any untoward medical occurrence associated with the use of a drug in humans, whether or not considered drug related, that occurs after a subject provides informed consent. Abnormal laboratory values or test results occurring after informed consent constitute AEs only if they induce clinical signs or symptoms, are considered clinically meaningful, require therapy (eg, hematologic abnormality that requires transfusion), or require changes in the study drug(s).

#### **8.1.2. Reporting**

Adverse events that begin or worsen after informed consent should be recorded on the Adverse Events form of the eCRF. Conditions that were already present at the time of informed consent should be recorded on the Medical History form in the eCRF. Monitoring for the occurrence of new AEs should be continued for at least 30 days after the last dose of study drug. Adverse events (including laboratory abnormalities that constitute AEs) should be described using a diagnosis whenever possible rather than by individual underlying signs and symptoms. When a clear diagnosis cannot be identified, each sign or symptom should be reported as a separate AE.

The term "disease progression" should be recorded as an AE/SAE only if there are no other identifiable AEs/SAEs associated with the disease progression at the time of reporting. For events associated with disease progression, the relevant signs and symptoms should be reported using a diagnosis whenever possible rather than individual underlying signs and symptoms. When a clear diagnosis cannot be identified, each sign or symptom should be reported as a separate AE. If the events resulting from disease progression meet the criteria for an SAE (eg, resulted in hospitalization, a life-threatening event, or death), the specific events(s) should be reported as an SAE(s) as described in Section 8.3.2. In both cases (ie, AEs or SAEs related to disease progression), it should be indicated that each event (reported as a diagnosis or as signs and symptoms) is related to disease progression on the Adverse Events form of the eCRF.

The severity of AEs will be assessed using CTCAE v4.03 Grades 1 through 4. The CTCAE v4.03 severity of Grade 5 will not be used; AEs resulting in death will be graded accordingly using Grades 1 through 4 and have the outcome noted as fatal. If an event is not classified by CTCAE the severity of the AE will be graded according to the scale below to estimate the grade of severity:

Grade 1	Mild; asymptomatic or mild symptoms; clinical or diagnostic observations only; intervention not indicated.
Grade 2	Moderate; minimal, local, or noninvasive intervention indicated; limiting age-appropriate activities of daily living.
Grade 3	Severe or medically significant but not immediately life-threatening; hospitalization or prolongation of hospitalization indicated; disabling; limiting self-care activities of daily living.
Grade 4	Life-threatening consequences; urgent intervention indicated.

The occurrence of AEs should be sought by nondirective questioning of the subject during the screening process after signing the ICF and at each visit during the study. Adverse events may also be detected when they are volunteered by the subject during the screening process or between visits, or through physical examination, laboratory test, or other assessments. To the extent possible, each AE should be evaluated to determine:

- The severity grade (CTCAE Grade 1 to 4).
- Whether there is at least a reasonable possibility that the AE is related to the study treatment: suspected (yes) or not suspected (no).
- The start and end dates, unless unresolved at final follow-up.
- The action taken with regard to study drug.
- The event outcome (eg, not recovered/not resolved, recovered/resolved, recovering/resolving, recovered/resolved with sequelae, fatal, unknown).
- The seriousness, as per serious AE (SAE) definition provided in Section 8.3.1.

Unlike routine safety assessments, SAEs are monitored continuously and have special reporting requirements (see Section 8.3.2).

All AEs should be treated appropriately. If an AE is treated with a concomitant medication or nondrug therapy, this action should be recorded on Adverse Event form and the treatment should be specified on the Prior/Concomitant Medications or Procedures and Non-Drug Therapy form in the eCRF.

Once an AE is detected, it should be followed until it has resolved or until it is judged to be permanent; assessment should be made at each visit (or more frequently if necessary) of any changes in severity, the suspected relationship to the study drug, the interventions required to treat the event, and the outcome.

When the severity of an AE changes over time for a reporting period (eg, between visits), each change in severity will be reported as a separate AE until the event resolves. For example, 2 separate AEs will be reported if a subject has Grade 1 diarrhea, meeting the definition of an AE, that lasts for 3 days before worsening to a Grade 3 severity. The Grade 1 event will be reported as an AE with a start date equal to the day the event met the Grade 1 AE definition and a stop date equal to the day that the event increased in severity from Grade 1 to Grade 3. The Grade 3 event will also be reported as an AE, with the start date equal to the day the event changed in intensity from Grade 1 to Grade 3 and a stop date equal to the day that the event either changed severity again or resolved.

